3.1.2. Category II

Subjects should have not received any collagenase treatments since the completion of double-blind study.

Subjects who showed an improvement in cellulite severity of at least two levels in at least one buttock in both the PR-PCSS and the CR-PCSS (ie, 2-level composite responder) in the double-blind study.

These subjects will be observed for time to reduction of response (defined in section 4.4.1) and safety approximately every 6 months for 2 years and will be observed annually for up to 3 years (Day 1080) from Day 71 of the double-blind study.

- Category II subjects must have at least 1-level composite response reduction (ie, reduction of response by at least 1-level in the PR-PCSS and CR-PCSS ratings) compared to Day 71 of the double-blind study (EN3835-302/303) AND no longer maintain 2-level composite response compared to baseline in the EN3835-302/303 study on either or both buttocks to be eligible for a retreatment course. If there is a composite worsening of cellulite severity, the confirmation of loss of response will be established during a follow-up visit ~2 weeks after the loss of response is detected at Day 180, if the loss of response is not confirmed then the subject will not be eligible for retreatment in this study.

One and only one retreatment course in up to 2 qualifying buttocks concurrently will be offered to eligible Category I and Category II subjects during this 3-year study. The subjects in Category I and/or eligible Category II subjects will receive a retreatment course consisting of 3 treatment sessions separated by 21 days (Day 1, 22, and 43). Each treatment session will consist of 12 injections (0.07 mg/0.3 mL per injection) of CCH for a dose of 0.84 mg and volume of 3.6 mL (identical to the treatment course administered in the double-blind study), in each qualifying buttock (see

Table 5) in up to two buttocks treated concurrently.

After initiation of retreatment, the safety and cellulite severity will be assessed on Days 22, 43, and 71. The Category I and Category II subjects who received retreatment will have safety assessment completed during the observational visits at Months 12, 18, 24, and 36 from Day 71 of the double-blind study.

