3.1.3. Category III

- Subjects who received active study drug in study EN3835-302 or EN3835-303 but did not meet criteria to be included in Category I or II (ie, non-composite responders).
- Category III subjects will not be eligible for retreatment in this study.

Assessment of open-label efficacy following retreatment will be determined up to Treatment Visit 4 (Day 71 + 5 days), after which all subjects (including the subjects who did not accept the offer of re-treatment) will be observed for safety every 6 months for 2 years and annually for up to 3 years (Day 1080) after Day 71 of the double-blind study.

The study schema is provided in Figure 1 below:

Figure 1: Study Design

The Schedule of Events for all subjects up through 180 days following the double-blind studies is provided in [Table 1](#).

Table 1: Schedule of Events Up to 180 Days

Procedures^a	Screening A^b (≥Day 71 Visit of Double-blind Study) (+14 days)	Visit 1 Day 180^c (±14 days) M6/Early Termination	Durability Confirmation Visit^d
Unblinding of Investigator, subject and site to subjects' treatments in EN3835-302/303 ^e		X	
Informed consent ^f	X	X	
Inclusion/exclusion	X		
Digital photography	X	X	X
Prior/concomitant medications/procedures ^g	X	X	
Physical examination:	X		
• Body weight	X	X	
• Height	X		
Vital signs	X	X	
Collection of Samples			
• Clinical laboratory	X	X	
• Anti-AUX-I/anti-AUX-II antibody level	X		
• Pregnancy testing ^h	X	X	
Subject Cellulite Assessments			
• Review assessments' training and use materials	X	X	X
• Patient Reported Photonumeric Cellulite Severity Scale (PR-PCSS) ^{ij}	X	X	X
• Subject Global Aesthetic Improvement (S-GAIS) ⁱ	X	X	
• Patient Reported Cellulite Impact Scale (PR-CIS)	X	X	
• Subject Satisfaction With Cellulite Treatment Assessment	X	X	
• Subject Self-Rating Scale (SSRS)	X	X	
Investigator Cellulite Assessments			
• Review assessment's training and use materials	X	X	X
• Clinician Reported Photonumeric Cellulite Severity Scale (CR-PCSS) ^k	X	X	X
Assignment of Subject to Category I, II, or III ^l		X	
Local safety assessments ^m	X	X	X
Adverse events ⁿ	Monitored throughout study		

Table 1: Schedule of Events Up to 180 Days (Continued)

FOOTNOTES:

- ^a Unscheduled visits may be done as deemed necessary at any time during the study to ensure subject safety; assessments done at unscheduled visits are at the discretion of the investigator. No photographs or cellulite severity assessments will be done at unscheduled visits.

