 - ⁱ Up to 4 hours before injection; approximately 15 and 30 minutes after injection. Pulse and blood pressure to be taken after subject has been sitting for 5 minutes. Vital signs must be stable before the subject is discharged. Refer to section 14.9 of Protocol Amendment 3.
 - ^j Do not conduct if Screening B visit date is within 12 months of obtaining an ECG during the double-blind study (EN3835-302/303).
 - ^k Serum pregnancy test on Screening visit and Day 71/EOS visit; urine pregnancy test on Day 1, Day 22, and Day 43 visits and Unscheduled Visit.
 - ^l Assessment made via photographs (if treatment visit, use photographs taken before marking dimples and injection sites).
 - ^m Subject assessments should be completed independently and prior to investigator assessments at each visit. Includes bot buttocks regardless of treatment, each buttock should be assessed independently.
 - ⁿ At least one of the Category I subject’s buttocks must have scores/ratings of at least 2 in both the CR-PCSS and PR-PCSS to be eligible to receive treatment. Category II subjects must have at least a 1-level composite response reduction compared to Day 71 of the EN3835-302/303 study AND no longer maintain a 2-level composite response compared to baseline in the EN3835-302/303 study on either or both buttocks.
 - ^o Local adverse events associated with the injection site, including acute (eg, erythema, bruising, pain, nodules/mass, ulceration, blistering, pruritus, swelling, and/or induration) and/or chronic (eg, skin thickening, fibrosclerosis, peau d’orange changes) cutaneous adverse events, will be recorded and evaluated for seriousness and severity.
- ECG=Electrocardiogram; EFP=Edematous fibrosclerotic panniculopathy; EOS=End of study; Tx=Treatment.

The Schedule of Events beyond Day 180 for subjects in Category I and II who are eligible and opted to receive retreatment, for the subjects in Category II who are not eligible for retreatment, and Category I and II subjects who are eligible but opted not to have retreatment is provided in [Table 3](#).

Table 3: Schedule of Events: Category I/II Subjects – Observation Assessments

	OBS Visit 2 Day 360 (±30 d) (M12)	OBS Visit 3 Day 540 (±30 d) (M18)	OBS Visit 4 Day 720 (±30 d) (M24)	OBS Visit 5 Day 1080/EOS/Early Termination (±30 d) (M36)	Durability Confirmation Visit^b
Procedures^a					
Verification of informed consent	X				
Inclusion/exclusion	X				
Digital photography	X	X	X	X	X

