2-level Composite Reduction	Worsening of cellulite severity improvement by at least 2-level on both PR-PCSS and CR-PCSS ratings compared to the score at Day 71/EOS (or Day 1) in the double-blind study.	Worsening of cellulite severity improvement by at least 2-level on both PR-PCSS and CR-PCSS ratings compared to the score at Day 71/End of Treatment Session in the open-label treatment phase.
1-level Composite Reduction	Worsening of cellulite severity improvement by only 1-level on both PR-PCSS and CR-PCSS ratings compared to the score at Day 71/EOS (or Day 1) in the double-blind study.	Worsening of cellulite severity improvement by only 1-level on both PR-PCSS and CR-PCSS ratings compared to the score at Day 71/End of Treatment Session in the open-label treatment phase.
Time to Composite Reduction of Response by 2-level	Number of days from the time of assessing composite improvement in cellulite severity on PR-PCSS and CR-PCSS at Day 71/EOS (or Day 1) in the double-blind study to the study visit prior to retreatment at which at least 2 level of worsening of response in both PR-PCSS and CR-PCSS ratings is observed for the first time.	Number of days from the time of assessing composite improvement in cellulite severity on PR-PCSS and CR-PCSS at Day 71/End of Treatment Session in the open-label treatment phase to the study visit during observation phase after retreatment at which at least 2 level of worsening of response in both PR-PCSS and CR-PCSS ratings is observed for the first time.
Time to Composite Reduction of Response by 1-level	Number of days from the time of assessing composite improvement in cellulite severity on PR-PCSS and CR-PCSS at Day 71/EOS (or Day 1) in the double-blind study to the study visit prior to retreatment at which only 1-level of worsening of response in both PR-PCSS and CR-PCSS ratings is observed for the first time.	Number of days from the time of assessing composite improvement in cellulite severity on PR-PCSS and CR-PCSS at Day 71/End of Treatment Session in the open-label treatment phase to the study visit during observation phase after retreatment at which only 1-level of worsening of response in both PR-PCSS and CR-PCSS ratings is observed for the first time.

Table 13: Reduction of Response (Continued)

Variables	Prior to Retreatment (including Through Day 180 Observational Period)	After Retreatment

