Baseline for Reduction of response and Improvement in Cellulite Severity (CR-PCSS and PR-PCSS)	
Improvement in Cellulite Severity: The assessment performed at Day 1 during the retreatment phase will be used as baseline to evaluate improvement in cellulite severity at Day 71 in this study.
 
Reduction of Response Prior to Retreatment: The assessment performed at Day 71/EOS visit in the double-blind phase will be used as baseline to evaluate reduction of response for any visits prior to/on first dose date of retreatment in this study.
 
Reduction of Response After Retreatment: The assessment performed at Day 71/End of treatment Session in the retreatment phase will be used as baseline to evaluate reduction of response during the observation phase after retreatment.

Baseline for CR-PCSS, PR-PCSS and PR-CIS Score	
At 180 Day Evaluation: The Screening assessment done within 14 days of Day 71/EOS of double-blind period will be used as baseline for 180 Day Evaluation period.
 
Before Retreatment: The Screening assessment done within 14 days of Day 71/EOS of double-blind period will be used as baseline for open-label period for subjects in TRR population who are not retreated, and until the point prior to retreatment for the subjects who are retreated.
 
After Retreatment: The assessments at Screening B/unscheduled assessment or Day 1 of the retreatment phase prior to/on the first dose date of retreatment in this study will be used as baseline.

Baseline for S-GAIS and Subject Satisfaction with Cellulite Treatment	The pretreatment Day 1 digital images from the double-blind study (EN3835-302/303) will be used as baseline.
Change from Baseline	Change from baseline will be derived as, post-baseline visit/time point value – the baseline value.
Time to reduction of response prior to retreatment (duration in days)	Date of visit where reduction is detected first – Date of Day 71/EOS of double-blinded studies 302/303
Time to reduction of response after retreatment (duration in days)	Date of visit where reduction is detected first – Date of Day 71/End of Treatment Session of open-label retreatment phase
Time to Complete Loss of Response prior to retreatment (duration in days)	Date of visit where complete loss of response reduction is detected first – Date of Day 71 of double-blinded studies 302/303 OR Date of Day 71/End of Treatment Session of open-label retreatment phase

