Time to Complete Loss of Response after retreatment (duration in days)	Date of visit where complete loss of response reduction is detected first – Date of Day 71/End of Treatment Session of open-label retreatment phase
Last Date in Study	End date of last visit where subject was seen by investigator. If subject was lost to follow-up, then last date of contact. If the subject had contact with the site after the final visit (eg, to follow-up on an AE), the last visit date will still be used as last date in the study.

Table 17: Derived Variables and Definition (Continued)

Variable	Definition
Time in Study	Last date in study – Date of Screening visit (relative day 1 overall study) + 1
Duration of AE	AE end date – AE start date + 1
AE Onset Day (retreatment phase)	AE start date - Date of first injection + 1
AE Onset Day (overall study)	AE start date - Date of Screening Visit (relative day 1 overall study) + 1

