7.6.2. Reduction of response using PR-PCSS and CR-PCSS Prior to Retreatment

The proportion of subjects or buttocks with reduction of response (refer to section 4.4.1) will be summarized using frequency counts and percentages using TRR Population Before Retreatment and OLNLR Population subject category (ie, Category I and II, and Overall) and treatment area (ie, left and/or buttock) at the following visits prior to retreatment: Day 180, Month 12, 18, 24, and 36 where reduction of response is assessed.

The proportions will be computed based upon number of subjects within each category and treatment area remains not-retreated prior to that visit.

The following efficacy end points for reduction of response will be summarized:

- Proportion of subjects with 2-level composite reduction
- Proportion of subjects with 1-level composite reduction
- Proportion of subjects with complete loss of response

The time to composite reduction of response (ie, by 1-level and 2-level separately) and time to complete loss of response (refer to section 4.4.1 for derivation) will be summarized descriptively using TRR Population Before Retreatment and OLNLR Population.

The listings of cellulite PR-PCSS and CR-PCSS severity ratings will be provided for All Subjects prior to retreatment.

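### Time to reduction of response is dated at the visit that first finds the loss, 6 to 12 months after the previous rating, so for areas that lose response it is an upper bound summarised as an ordinary duration

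*SAP*

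**What the plan says.** Time to reduction of response (TRR) is the only secondary objective (SAP 2.2). Table 17 in Section 6.2 derives it as the "Date of visit where reduction is detected first" minus the date of double-blind Day 71/EOS or, after retreatment, minus the date of Day 71 of the retreatment course. Complete loss follows the same pattern: "Date of visit where complete loss of response reduction is detected first". Table 13 in Section 4.4.2 agrees; it counts days to the study visit at which worsening in both "ratings is observed for the first time".

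Section 7.6.2 lists the assessment visits before retreatment as "Day 180, Month 12, 18, 24, and 36 where reduction of response is assessed". The schedule tables allow ±14 days at Day 180 and ±30 days at later visits, and their footnotes exclude severity ratings at unscheduled visits. Sections 7.6.2 and 7.6.3 summarise the times descriptively, which under Section 6.1 means n, mean, SD or SE, median, minimum and maximum. The SAP does not record the last visit without loss, name an interval-censored method, or label the variable as time to detection.

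**The concern.** A loss found at one visit happened at some unknown point since the previous rated visit. The plan keeps only the right end of that interval and then takes means and medians of it. Recorded times therefore cluster at visit days, and their values depend partly on the schedule. A loss on Day 725 is recorded at about Day 1080.

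A mean or median time to reduction is naturally read as how long the response lasted. For areas that lose response, that reading overstates the time. Better handling of areas that do not lose response would not cure this: a Kaplan-Meier curve on the same detection dates would still place each loss at the right end of its interval.

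**Working it through.** **Plan's own figure.** There is none to reproduce. The SAP gives no expected time, event count or loss rate, and its sample of about 420 (Section 3.6) is a rollover count.

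**Gaps, from the schedule.** Nominal visits at 0 (double-blind Day 71), 180, 360, 540, 720 and 1080 days give gaps of 180, 180, 180, 180 and 360 days. With the windows, the widest gaps are 194 (180+14), 224 (390−166), 240 (570−330), 240 (750−510) and 420 (1110−690) days.

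**Direction.** If T is the true time of loss, a and b are adjacent rated visits, and a < T ≤ b, the rule records b. With accurate ratings b − T is never negative. This needs no assumption about the distribution of T.

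**Size, under assumptions.** Take T exponential with rate λ = ln 2 / median, ratings without error, nominal visits, and every area followed to Day 1080. Within an interval of width w, the mean excess is w / (1 − exp(−λw)) − 1/λ.

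- Median 300: 1/λ = 432.8. For w = 180: 180/0.3403 − 432.8 = 96 days. For w = 360: 360/0.5647 − 432.8 = 205 days.
- Median 800: 1/λ = 1154.2. For w = 180: 180/0.1444 − 1154.2 = 92 days. For w = 360: 360/0.2680 − 1154.2 = 189 days.

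The interval probabilities, exp(−λa) − exp(−λb) divided by the probability of loss by Day 1080, weight these excesses. For median 300 the weights are 0.371, 0.245, 0.161, 0.106 and 0.117. The mean excess is 0.883 × 96.2 + 0.117 × 204.7 = 109 days.

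| Assumed true median (days) | Lost by Day 1080 | True mean among lost | Mean under Table 17 | Excess | Excess / true mean |
|---|---|---|---|---|---|
| 300 | 92% | 336 | 445 | 109 | 32% |
| 500 | 78% | 410 | 523 | 113 | 27% |
| 800 | 61% | 457 | 572 | 115 | 25% |

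A separate simulation of 400,000 areas per scenario, with assumed medians from 180 to 2000 days, gave mean excesses of 106 to 118 days.

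**Imperfect ratings.** Table 17 does not tie the event date to the confirmation visit about 14 days later. With an assumed false detection rate of 2% to 10% per visit, and medians of 360 to 1080 days, about 3% to 18% of areas truly lost by Day 1080 receive a date before the true loss. The mean excess falls to 30 to 98 days but stays positive.

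**Whole cohort.** Areas with no detected loss have no Table 17 value, so the summary covers only areas that lost response.

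| True median, all areas | Reported median | True mean, all areas | Reported mean |
|---|---|---|---|
| 300 | 360 | 433 | 445 |
| 500 | 360 | 721 | 523 |
| 800 | 540 | 1154 | 572 |

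In the second and third rows the reported figures lie below whole-cohort durability, although each recorded time is too long for its own area.

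**After the fix.** In the simulation, an exponential interval-censored likelihood with areas not lost right-censored at Day 1080 returned medians of 180, 359, 721, 1076 and 2006 days for true values of 180, 360, 720, 1080 and 2000.

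**The case against.** The strongest reply is that this is a single-arm, descriptive endpoint with no test. Tables 13 and 17 openly define it as the visit of first detection, and dating an event when it is first documented is a common convention. Sections 7.6.2 and 7.6.3 also tabulate proportions with reduction at each visit, which conveys part of the same information. This keeps the point at the level of a worthwhile improvement. It does not remove it: nothing tells the reader of a mean time to reduction that it is an upper bound, and the visit proportions are not the percent first lost in each interval.

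The size is open to challenge too. Ratings at Screening B, treatment Day 1 and early termination shorten some gaps. A footnote to Table 1 also foresees ratings at an unscheduled unblinding visit. In the example in Section 3.1.2, the first gap after retreatment is 119 days (Day 421 to Day 540). Areas that are retreated leave the analysis before retreatment early, often before the 360-day gap. These features lower the average excess but leave the detection date at the right end of its interval.

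A reader might infer that every recorded time is too long, or that the plan always favours longer durability and a correction must shorten it. The document supports neither. An unconfirmed first detection can date a loss too early, and omitting areas without loss works in the opposite direction.

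**Conclusion.** The point holds for areas that lose response. The plan records the right end of a 6- to 12-month interval as the time of loss for its only secondary objective and summarises it without interval bounds or a label.

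The upward direction for these areas rests on accurate ratings alone. The size, about 109 to 115 days on the mean, rests on exponential loss with medians of 300 to 800 days, perfect ratings, nominal visits and follow-up of every area to Day 1080. The SAP gives no loss rate to replace those assumptions. Extra ratings, earlier exit to retreatment or false first detections would make it smaller.

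For the cohort as a whole, the net direction is not fixed, because leaving out areas without loss biases durability downward. The two errors should not be counted on to cancel.

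**What to change.** For each area, derive the interval from the last rated visit without the reduction (exclusive) to the first rated visit with it (inclusive). A rated visit should mean one where both components are present, since Section 6.3 sets the composite to missing otherwise. Right-censor areas with no loss at their last rated visit before retreatment or end of follow-up. Report a Turnbull curve and median in place of the mean and median of detection days, for reduction and for complete loss, before and after retreatment.

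If only descriptive tables are wanted, report the percent of areas first lost in each visit interval and rename the Table 17 variables as time to first detection (upper bound).

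Both options use ratings already collected. The cost is SAP wording and one procedure, which SAS 9.4 provides (PROC ICLIFETEST). Estimates will be less precise, and stated durability may become shorter or longer.

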4.4.2. Reduction / Improvement of Response in Cellulite Severity Scale (PR-PCSS and CR-PCSS)

Reduction of Response will be assessed separately for prior to retreatment (including Through Day 180 Observational Period) and after retreatment. Refer below Table 13 for definitions of reduction of response:

Table 13: Reduction of Response

Variables	Prior to Retreatment (including Through Day 180 Observational Period)	After Retreatment
Reduction of Response	Worsening of cellulite severity improvement on PR-PCSS or CR-PCSS ratings in this study prior to retreatment compared to the score at Day 71/EOS (or Day 1) in the double-blind study. This reduction is also referred as a Partial Loss of Response.	Worsening of cellulite severity improvement on PR-PCSS or CR-PCSS ratings during the observation phase after retreatment compared to the score at Day 71/End of Treatment Session in the open-label treatment phase.
2-level Reduction	Worsening of cellulite severity improvement at least by 2-level on PR-PCSS or CR-PCSS ratings in this study prior to retreatment, compared to the score at Day 71/EOS (or Day 1) in the double-blind study (ie, change from baseline PR-PCSS and/or CR-PCSS rating of 2, 3, or 4)	Worsening of cellulite severity improvement at least by 2-level on PR-PCSS or CR-PCSS ratings during the observation phase after retreatment compared to the score at Day 71/End of Treatment Session in the open-label treatment phase (ie, change from baseline PR-PCSS and/or CR-PCSS rating of 2, 3, or 4)
1-level Reduction	Worsening of cellulite severity improvement by only 1-level on PR-PCSS or CR-PCSS ratings in this study after retreatment compared to the score at Day 71/EOS (or Day 1) in the double-blind study (ie, change from baseline PR-PCSS and/or CR-PCSS rating of 1)	Worsening of cellulite severity improvement only by 1-level on PR-PCSS or CR-PCSS ratings during the observation phase after retreatment compared to the score at Day 71/End of Treatment Session in the open-label treatment phase (ie, change from baseline PR-PCSS and/or CR-PCSS rating of 1)
Composite Reduction	Composite Reduction will be assessed using both the subject PR-PCSS responder classification and investigator CR-PCSS responder, where both the scales have same level of reduction. If the classification is missing for 1 or both components (ie, the PR-PCSS component or the CR-PCSS component), then the composite responder classification is missing for that visit.	

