Complete Loss of Response	Worsening of cellulite severity improvement on PR-PCSS and CR-PCSS ratings in this study prior to retreatment compared to the score at Day 71/EOS in the double-blind studies, where cellulite severity returns to baseline levels of the double-blind studies (ie, Day 1 of the double-blind studies) or worse.	Worsening of cellulite severity improvement on PR-PCSS and CR-PCSS ratings compared to the score at Day 71/End of Treatment Session in the open-label treatment phase, where cellulite severity returns to baseline levels of the retreatment phase (ie, Day 1 of the open-label retreatment phase) or worse.
Time to Complete Loss of Response	Number of days from the time of assessing composite improvement in cellulite severity on PR-PCSS and CR-PCSS at Day 71/EOS in the double-blind study to the study visit prior to retreatment at which the complete loss of response in both PR-PCSS and CR-PCSS is observed.	Number of days from the time of assessing composite improvement in cellulite severity on PR-PCSS and CR-PCSS at Day 71/End of Treatment Session in the open-label treatment phase to the study visit during observation phase after retreatment at which the complete loss of response in both PR-PCSS and CR-PCSS is observed.
2-level Improvement	Improvement in cellulite severity at least by 2 levels on PR-PCSS or CR-PCSS ratings from Day 1 of double-blind study (ie, change from baseline PR-PCSS and/or CR-PCSS rating of -2, or -3).	Improvement in cellulite severity at least by 2 levels on PR-PCSS or CR-PCSS ratings after receiving the retreatments compared to the corresponding rating at Day 1 of the Treatment Session of this study (ie, change from baseline PR-PCSS and/or CR-PCSS rating of -2, or -3).
1-level Improvement	Improvement in cellulite severity at least by 1 levels on PR-PCSS or CR-PCSS ratings from Day 1 of double-blind study (ie, change from baseline PR-PCSS and/or CR-PCSS rating of -2, or -3).	Improvement in cellulite severity at least by 1 levels on PR-PCSS or CR-PCSS ratings after receiving the retreatments compared to the corresponding rating at Day 1 of the Treatment Session of this study (ie, change from baseline PR-PCSS and/or CR-PCSS rating of -2, or -3).

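### Table 17 allows time to complete loss of response before retreatment to be counted from the end of the later retreatment course, which can give a negative or wrong-phase duration

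*SAP*

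**What the plan says.** Table 17 (section 6.2) has two rows for time to complete loss of response. The row for the period before retreatment takes the first visit with complete loss and subtracts "Date of Day 71 of double-blinded studies 302/303 OR Date of Day 71/End of Treatment Session of open-label retreatment phase". The row for the period after retreatment reads "Date of visit where complete loss of response reduction is detected first – Date of Day 71/End of Treatment Session of open-label retreatment phase".

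Table 13 (section 4.4.2) defines the same pre-retreatment variable with one origin. It counts from the assessment "at Day 71/EOS in the double-blind study to the study visit prior to retreatment at which the complete loss of response" is observed.

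Section 7.6.2 reports the variable: "time to complete loss of response (refer to section 4.4.1 for derivation) will be summarized descriptively using TRR Population Before Retreatment", and also in the population not retreated.

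Separately, the pre-retreatment column of Table 13 defines 1-level reduction as worsening "by only 1-level on PR-PCSS or CR-PCSS ratings in this study after retreatment compared to the score at Day 71/EOS" of the double-blind study. The 2-level row directly above it, in the same column, refers to ratings before retreatment.

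**The concern.** A time to event needs one origin, and the origin must precede the event. This row offers two, joined by OR. The second is the end-of-treatment visit of a course that, for a pre-retreatment loss, has not yet begun.

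The subjects for whom the choice arises matter for durability. The TRR Population Before Retreatment includes subjects who are retreated later, with their data up to retreatment (section 8, Table 18). Category II subjects qualify for retreatment only after a confirmed reduction of response, so those who lose response are likely to have a second date on file.

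Time to reduction of response is the study's only secondary objective, and time to complete loss is one of the durations summarised for it in section 7.6.2. The summaries are means, medians, minima and maxima (section 6.1), so a wrongly derived value would enter them directly.

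**Working it through.** **Inputs**
- Two permitted origins: double-blind Day 71 (A) and Day 71/end of treatment of the retreatment course (B). Source: Table 17.
- Retreatment timing: section 3.1.2 gives an example that starts on Day 351 and reaches Treatment Visit 4 on Day 421. Observation days are taken as counted from double-blind Day 71, as in that section.
- Treatment Visit 4 is retreatment Day 71, with a window of +5 days (Table 2).

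**The SAP's own figure.** Retreatment Day 71 = start + 71 - 1 = 351 + 70 = 421. This matches.

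**Duration under each origin**, as loss visit day minus origin day, for the subject in the example:

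| Loss first seen | Origin A | Origin B |
|---|---|---|
| Day 180 | 180 - 0 = 180 | 180 - 421 = -241 |
| Day 351 (retreatment Day 1, before injection) | 351 - 0 = 351 | 351 - 421 = -70 |

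**General bound.** A pre-retreatment visit falls on or before the first retreatment dose. For a completed course, origin B falls 70 to 75 days after that dose. At nominal timing the duration under B is therefore -70 days or less.

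**B does not measure durability.** Assume that retreatment starts 14 days after the scheduled visit at which loss is seen. Then B gives -(14 + 70) = -84 days whether that visit was Day 180, 360, 540 or 720. Origin A gives 180, 360, 540 and 720.

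**When B is positive.** The loss visit must then follow the retreatment course. In the SAP's example the next observation visit is Day 540, and 540 - 421 = 119 days. That is the value the after-retreatment row already produces, so it would place a second-course result in a first-course variable.

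**Neighbouring definitions**
- Time to reduction before retreatment, Table 17: "Date of visit where reduction is detected first – Date of Day 71/EOS of double-blinded studies 302/303". It has one origin and no alternative.
- Table 17 baseline rule: the double-blind Day 71/EOS assessment "will be used as baseline to evaluate reduction of response for any visits prior to/on first dose date of retreatment in this study".
- Times to 1-level and 2-level composite reduction, Table 13: both end at a visit before retreatment.
- Cross-reference: section 7.6.2 sends the reader to 4.4.1 for the derivation. That section defines only change scores; the time variables are in 4.4.2.

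The row for complete loss is the only pre-retreatment duration that admits B.

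**The 1-level cell in Table 13.** It defines reduction on a single scale. Before retreatment, section 7.6.2 lists 2-level composite reduction, 1-level composite reduction and complete loss. The 1-level composite row does not carry the misplaced phase wording. Single-scale reductions are listed only in section 7.6.3, after retreatment, which uses the other column.

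**The case against.** The strongest reply is that the SAP gives the right rule elsewhere. Table 13 is unambiguous, it sits in the section group to which 7.6.2 points, and the Table 17 baseline rule agrees with it. A careful programmer would use double-blind Day 71, and a negative minimum would show in the output. The alternative looks like a remnant of a row that once covered both phases, although that is inference.

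Most of this stands. The wrong result is permitted, not forced. A subject never retreated has no second date, so the summary in the not-retreated population is unaffected.

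It does not remove the defect. Table 17 is presented as the listing of derived variables and their definitions, it conflicts with Table 13, and the section cited in 7.6.2 contains neither rule. A visible minimum would reveal negative values but not a positive duration taken from the wrong phase.

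A reader might infer that pre-retreatment durability as a whole comes out negative, or that mean durability shrinks by some stated amount. The SAP supports neither. The reduction-time rows are sound, and the document does not say how many subjects with complete loss are retreated, so no shift in a mean can be derived. A reader might also infer that the 1-level slip credits the retreatment effect to the first course in a reported endpoint. No endpoint bulleted in 7.6.2 uses that cell.

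**Conclusion.** The pre-retreatment row for complete loss in Table 17 is a wrong derivation rule. Its second origin contradicts Table 13, repeats the next row, and gives a negative or wrong-phase duration whenever it is used. In the SAP's own example the error is 421 days: -241 instead of 180, or -70 instead of 351.

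The reach is narrow: one duration variable, and only subjects who are later retreated. The bound of -70 days assumes a completed course at nominal timing; an early-termination visit used as end of treatment would shorten the gap. The analyses are descriptive, so no test or error rate is involved.

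The Table 13 slip is real but minor.

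**What to change.** In Table 17, in the row for time to complete loss before retreatment, delete the word OR and the retreatment Day 71/end-of-treatment date after it. Double-blind Day 71 is then the only origin, as in Table 13.

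In Table 13, 1-level reduction, pre-retreatment column, change the phase of the ratings from after retreatment to prior to retreatment, to match the 2-level row and the column heading.

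It would help to point the derivation reference in section 7.6.2 to 4.4.2 at the same time.

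The cost is a few words in the SAP and a check that any existing program uses the single origin. No new data are needed, and no clinical rule changes.
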